2 STUDY OVERVIEW

2.1 Synopsis of study design

[figure not shown]
ALN-AT3SC-004 (EFC14769) is a multicenter, multinational, randomized, open-label Phase 3 study designed to evaluate the efficacy and safety of fitusiran in male patients aged ≥ 12 years with hemophilia A or B, without inhibitory antibodies to FVIII or FIX, who are not receiving prophylactic therapy.

Eligible patients will be randomized in a 2:1 ratio to:

- **Fitusiran treatment arm:** Fitusiran 80 mg administered SC as prophylaxis once monthly, with use of on-demand factor concentrates of breakthrough bleeding episodes
- **On-demand arm:** On-demand factor concentrates for treatment of breakthrough bleeding episodes

The study design schema is presented in [Figure 1](#).

Figure 1 - Study design

Abbreviations: HA/HB = hemophilia Type A/hemophilia Type B; R = randomized

^a On-demand factor concentrates as routinely prescribed by physician per local standard practice.

^b Fitusiran treatment arm patients who do not enroll in the extension study: AT activity level will be monitored at monthly intervals following the final fitusiran dose until returning to activity levels return to approximately 60% (per the central laboratory) or per Investigator discretion in consultation with the study Medical Monitor.

2.2 Randomization methodology

Patients are randomized 2:1 to the fitusiran treatment arm and the on-demand arm. Randomization is stratified by the number of bleeding episodes in the 6 months prior to Screening (≤ 10 vs > 10) and hemophilia type (hemophilia A or B).

2.3 Unblinding

Although this is an open-label study, Sponsor personnel will not have access to efficacy summaries by treatment arms prior to conducting the formal reporting of the study.

2.4 Study procedures

The schedule of assessments is described in the study protocol ([Table 1](#)).

2.5 Modifications to the statistical section of the protocol

This section summarizes major changes to the protocol statistical section. These changes are made before the first patient is randomized. The statistical analysis plan history table below gives the timing, rationale, and key details for major changes to the protocol statistical section.

The first patient was enrolled on March 1, 2018. There are no planned interim analyses.

Protocol Amendment statistical changes

Amendment number	Date approved	Rationale	Description of statistical changes
1	16-Nov-2017	Revised the definition of efficacy period based on on-treatment strategy for the primary analysis of primary endpoint in assessing the primary objective of the study (ICH E9 (R1)).	Efficacy period (Day 29 to Day 246) defined in the protocol is changed to (Day 29, earliest of (Day 246, or the last day of bleeding follow up) excluding the period for each intercurrent event.
1	16-Nov-2017	Added exclusion periods due to fitusiran treatment discontinuation, major or minor surgery, prophylactic treatment with emicizumab or factor since including bleeding events in these periods in the primary analysis would bias fitusiran treatment effect.	Exclusion period for each intercurrent event is described in details in Section 6.3

[figure not shown]
[figure not shown]
2.6 Statistical modifications made in the statistical analysis plan

This section summarizes major changes in statistical analysis features made in approved SAP versions from statistical considerations in protocol or previous SAP versions, with emphasis on changes after study start (after the first patient was enrolled). These changes are made before database lock.

The statistical analysis plan history table below gives the timing, rationale, and key details for major changes to the statistical analysis features in the statistical analysis plan.

Statistical analysis plan statistical changes

SAP version number	Date approved	Rationale	Description of statistical changes
2	06-Aug-2019		The sensitivity analysis to include all bleeding events was added in Section 6.3.1.2.
2	06-Aug-2019		The summary statistics for number of patients who lost-to-follow-up and who had each intercurrent event is added in Section 6.3
2	06-Aug-2019		A summary of missing data pattern by treatment arm for patient who doesn't have bleeding data after Day 28 is added in Section 6.3.1.1. A sensitivity analysis based on imputed bleeding data in the efficacy period using multiple imputation (MI) method is added in Section 6.3.1.1.
2	06-Aug-2019		A sensitivity analysis based on zero-inflated negative binomial model is added in Section 6.3.1.2.

SAP version number	Date approved	Rationale	Description of statistical changes
2	06-Aug-2019	To be aligned with protocol amendment 02	The secondary endpoint ‘Change in Haem-A-QOL scores in the treatment period’ is changed to ‘Change in Haem-A-QOL physical health score and total score in the treatment period’ in Section 3.2.1 and Section 5.7. The analysis of physical health score is added in Section 6.3.2.4.
2	06-Aug-2019	To clarify how to calculate domain score when item scores are missing for Haem-A-QOL and Haemo-QOL assessments.	The method to calculate domain score when item scores are missing for Haem-A-QOL and Haemo-QOL assessments is added in Section 8.1.
2	06-Aug-2019		For the change in Haem-A-QOL physical health score and total score, the examination of normality assumption based on ANCOVA model and sensitivity analysis based on the non-parametric Wilcoxon-Mann-Whitney test are added in Section 6.3.2.4. In addition, a sensitivity analysis to handle missing assessment is also specified in Section 6.3.2.4.
2	06-Aug-2019	To clarify ANCOVA analysis for Haemo-QOL for small sample size	Clarify that only the descriptive statistics will be provided if ANCOVA model does not converge due to small sample size in Section 6.3.3.4.
2	06-Aug-2019		An exploratory analysis to evaluate the association between the change in Haem-A-QOL physical health and total scores and ABR and concomitant pain medication use is added in Section 6.3.2.4.
2	06-Aug-2019		An exploratory analysis of bleeding symptoms is added in Section 6.3.1.3.

SAP version number	Date approved	Rationale	Description of statistical changes
2	06-Aug-2019	To be aligned with protocol amendment 02	“Adverse events of clinical interest (AECI)” is changed to “Adverse events of special interest (AESI)” throughout. Systemic injection associated reactions (IARs) is added to the criteria of AESI in Section 6.6.2.
2	06-Aug-2019	To be aligned with Sanofi’s standard analysis for Lab and vital sign.	Lab analysis by NCI CTCAE grade and shift tables are removed in Section 6.6.3 since PCSA analysis will be performed. Vital sign by PCSA is added in Section 6.6.4.
2	06-Aug-2019	To align the analysis reference date with Day 1 visit date when baseline assessments are done, fitusiran first dose is given, and eDiary is distributed to the patients.	The reference date is changed from randomization to Day 1 visit date in Section 5.2. The baseline definition is changed from randomization to Day 1 visit in Section 5.5.
2	06-Aug-2019	To define geographic regions	Geographic regions are defined in Section 5.11.
2	06-Aug-2019	AT lowering capacity of fitusiran is expected to achieve therapeutic target range at the end of the onset period for the 80 mg fixed dose. ABR by AT lowering analysis does not add much value to the ABR comparison between onset period and efficacy period.	The analysis of ABR by AT lowering in Section 6.4.3 is removed.
2	06-Aug-2019	In addition to the primary analysis of ABR for the recurrence of events, it is also of interest to compare the time to first bleeding event between on-demand treatment and fitusiran prophylaxis treatment.	The exploratory analysis of time to first bleeding event is added in Section 6.3.1.3

SAP version number	Date approved	Rationale	Description of statistical changes
2	06-Aug-2019	To include untreated bleed in the bleeding episode definition	The untreated bleed is included in the bleeding episode definition in Section 6.3.
3	This version	To update Per-protocol Analysis Set definition	The detail deviations are included in the Per-protocol analysis set definition in Section 4.
3	This version	To define Covid-19 Unaffected Set	Covid-19 Unaffected Set is defined in Section 4.
3	This version	To clarify baseline definition for fitusiran group	For fitusiran group only, baseline definition is changed from Day 1 to first dose date in Section 5.5
3	This version	To clarify the multiplicity adjustment for Haem-A-QOL endpoints	For the two Haem-A-QOL scores (physical health score and total score), physical score will be tested first followed by total score.
3	This version	To add patient disposition category for Covid-19 impact summary	Patients discontinue the treatment due to Covid-19 and patient discontinue the study due to Covid-19 are added in Section 6.1
3	This version	Due to the exclusion criteria 6, the analysis of fibroscan/fibrotest result at baseline against worst post-baseline ALT elevation is not necessary	The related analysis is removed in Section 6.6.3
3	This version	To add the efficacy analyses for ABR endpoints due to Covid-19 impact	For ABR, the sensitivity analyses on Covid-19 unaffected set is added in Section 6.3. In addition, a sensitivity analysis to exclude the bleeds during the period of missing at least 2 consecutive doses due to Covid-19 event is added in Section 6.3.

SAP version number	Date approved	Rationale	Description of statistical changes
3	This version	To update the analyses for Haem-A-QoL due to Covid-19 impact	For sensitivity analyses, ANCOVA model will be ran on Covid-19 unaffected set, on the set excluding data collected with Covid-19 impact, on the set of patients whose responses level to EQ-5D dimensions “anxiety/depression” is no change or improved from baseline.
3	This version	To add the sensitivity analysis for Haem-A-QoL baseline assessments	For sensitivity analyses, the same analysis as main but excluding values of those who completed Haem-A-QOL at baseline on the same day but after first dose of fitusiran.
3	This version	To add the AE summary related to COVID-19 infection	AE potentially consistent with COVID-19 will be summarized by SOC and PT and list will also be provided. The search term list is added in the Appendix 8.2
3	This version	To add AE summary by hemophilia type	By hemophilia type summary is added to key AE tables.

3 OBJECTIVES AND ENDPOINTS

3.1 Objectives

3.1.1 Primary objective

- To evaluate the efficacy of fitusiran compared to on-demand treatment with factor concentrates, as determined by the frequency of bleeding episodes.

3.1.2 Secondary objectives

- To evaluate the efficacy of fitusiran compared to on-demand treatment with factor concentrates, as determined by:
 - The frequency of spontaneous bleeding episodes
 - The frequency of joint bleeding episodes
 - Health-related quality of life (HRQOL) in patients ≥ 17 years of age
- To determine the frequency of bleeding episodes during the onset period
- To determine the safety and tolerability of fitusiran

3.1.3 Exploratory objectives

- To evaluate the effects of fitusiran as compared to on-demand treatment with factor concentrates on the following patient reported outcomes:
 - Patient satisfaction with treatment
 - Patient activity
 - HRQOL in adolescents (≥ 12 to < 17 years of age)
- To determine the pharmacodynamic (PD) effect, pharmacokinetics (PK), and immunogenicity of fitusiran
- To evaluate the effects of fitusiran as compared to on-demand treatment with factor concentrates on the total weight-adjusted consumption of factor concentrates
- To evaluate the effects of fitusiran as compared to on-demand treatment with factor concentrates on joint status
- To evaluate the effects of fitusiran as compared to on-demand treatment with factor concentrates on patient resource use

3.2 Endpoints

3.2.1 Efficacy endpoints

Primary and secondary endpoints for Global and US protocols are in the table below

	Global Protocol	US Protocol
Primary	Annualized Bleeding Rate (ABR) in the efficacy period	ABR in the treatment period
Secondary	ABR in the treatment period	ABR in the efficacy period
	Annualized spontaneous bleeding rate in the efficacy period	
	Annualized joint bleeding rate in the efficacy period	
	Change in Haem-A-QOL physical health score and total score in the treatment period	
	ABR in the onset period	

Exploratory Efficacy Endpoints

- Change in the following in the treatment period:
 - Treatment Satisfaction Questionnaire for Medication (TSQM) domain scores
 - Haemophilia Activities List (HAL) score
 - Paediatric HAL (pedHAL) score
 - EQ-5D-5L index value and visual analogue scale (VAS) score
 - Haemo-QOL score
 - Hemophilia Joint Health Score (HJHS)
- Number of target joint bleeding episodes
- Annualized weight-adjusted use of factor concentrates
- Change in patient resource use (eg, work/school attendance, visits to doctor/hospital)

3.2.2 Pharmacokinetic endpoints

- All patients
 - Plasma PK parameters will be estimated using a population PK approach. The population PK analysis will be described in a separate population PK analysis plan.
- Patients from East Asian sites only

- In addition to population PK analysis, plasma PK parameters for the patients from the East Asian sites only will also be estimated using non-compartmental analysis. The plasma PK parameters will include, but may not be limited to:
 - Maximum plasma concentration (C_{max})
 - Time to maximum plasma concentration (t_{max})
 - Elimination half-life (t_{1/2β})
 - Area under the concentration-time curve (AUC)
 - Apparent clearance (CL/F)
 - Apparent volume of distribution (V/F)
- Fitusiran levels in 0-24 h urine will be reported as cumulative amount of drug excreted unchanged in urine (A_e).
- Additional PK parameters for plasma and/or urine may also be calculated, if considered appropriate.

3.2.3 Pharmacodynamic endpoints

- AT activity level over time
- Thrombin generation over time

3.2.4 Safety endpoints

- Adverse events
- Concomitant medications
- Clinical laboratory parameters
- Vital signs
- 12-lead ECGs
- Physical examinations

3.2.5 Anti-drug antibody endpoints

- Incidence and titer of antidrug antibodies to fitusiran in the fitusiran treatment arm

4 PATIENT POPULATION

The populations (analysis sets) are defined as follows:

- Intent-to-treat (ITT) Analysis Set: All randomized patients. All by-treatment analyses based on the ITT analysis set will be performed according to the randomized treatment arm. Efficacy Analyses will be conducted using the ITT Analysis Set unless otherwise specified.
- Safety Analysis Set: All patients who received at least 1 dose of study drug or were randomized to on-demand arm. All by-treatment analyses based on the safety analysis set will be according to the actual treatment received. Safety Analyses will be conducted using the Safety Analysis Set unless otherwise specified.
- Per-protocol Analysis Set: All patients in the ITT set who do not have protocol deviations in the following categories:
 - Failure to meet key eligibility criteria, which will be identified prior to database lock.
 - Actual treatment differs from IRS treatment assignment
 - Prophylactic use of factor
 - Other protocol deviations that might significantly affect the completeness, accuracy, and/or reliability of the bleeding data.

The major or critical detail deviations included are as follows.

- The subject is not male and/or is younger than 12 years, but the subject was randomized.
- The subject does not have severe hemophilia A or B without inhibitors as evidence by:
 - A laboratory FVIII level $<1\%$ or FIX level $\leq 2\%$ at Screening.
 - On-demand use of factor concentrate to manage bleeding episodes for at least the last 6 months prior to Screening, or meeting one of the following criteria:
 - Nijmegen-modified Bethesda assay inhibitor titer of <0.6 BU/mL at Screening,
 - No use of bypassing agents to treat bleeding episodes for at least the last 6 months prior to screening
 - No history of immune tolerance induction therapy within the last 3 years prior to Screening,but the subject was randomized.
- The subject does not have a minimum of 6 bleeding episodes requiring factor concentrate treatment within the last 6 months prior to Screening, but the subject was randomized.
- The subject has known co-existing bleeding disorders other than hemophilia A or B, but the subject was randomized.
- The subject currently uses factor concentrates as regularly administered prophylaxis designed to prevent spontaneous bleeding episodes, but subject was randomized.

- The subject's actual treatment differs from randomization group.
 - Site provided incorrect stratification data in IRT for patient's randomization.
 - The subject initiated use of factor concentrates or bypassing agents as prophylaxis for bleeding episode prevention, including doses related to anticipated hemostatic challenges such as physical activity, during the treatment period but the study drug was not discontinued.
- PK Analysis Set: All patients who receive at least 1 dose of study drug and have evaluable PK data contributing to the estimation of PK parameters.
 - Operative Procedure Analysis Set: All patients who received at least 1 dose of study drug or were randomized to on-demand arm and underwent at least 1 operative procedure during the study.
 - Covid-19 Unaffected Set: All patients who had no major or critical protocol deviations due to Covid-19 at any visits up to end of study (Month 9).

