Patients from both the fitusiran and on-demand treatment arms who complete the study may be eligible for participation in an open-label extension study. Following final fitusiran dose, for patients in the fitusiran treatment arm patients who do not enroll in the extension study, AT activity level will be monitored at monthly intervals until returning to an activity level of approximately 60% (per the central laboratory) or per Investigator discretion in consultation with the study Medical Monitor.

Number of Planned Patients

Approximately 120 patients will be randomized, including approximately 26 patients with hemophilia B and approximately 10 adolescents (≥ 12 to < 18 years of age).

Diagnosis and Main Eligibility Criteria

This study will include males with severe hemophilia A or B without inhibitors (defined as Nijmegen modified Bethesda assay inhibitor titer of <0.6 BU/mL at Screening), aged ≥ 12 years, who have had a minimum of 6 bleeding episodes requiring on-demand treatment with factor concentrates within the last 6 months prior to Screening. Diagnosis of severe hemophilia A or B will be based on a central laboratory measurement or documented medical record evidence of FVIII level $<1\%$ or FIX level $\leq 2\%$.

Investigational Product, Dose and Mode of Administration

Fitusiran is an SC administered N-Acetylgalactosamine (GalNAc)-conjugated siRNA targeting liver-expressed messenger RNA (mRNA) for AT.

Patients randomized to the fitusiran treatment arm will receive open-label fitusiran 80 mg as an SC injection once monthly for a total of 9 months; dosing will begin on Day 1 of the treatment period.

Reference Therapy, Dose and Mode of Administration

Patients in the on-demand arm will receive on-demand factor concentrate therapy per Investigator discretion to treat bleeding episodes from Day 1 through end of study. The protocol will recommend guidance for patients in the fitusiran treatment arm to use reduced initial doses of factor concentrates for breakthrough bleeding episodes during the fitusiran efficacy period.

Duration of Treatment

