5. SELECTION AND WITHDRAWAL OF PATIENTS

5.1. Inclusion Criteria

Each patient must meet all of the following inclusion criteria to be eligible for enrollment in the study:

1. Males \geq 12 years of age.
2. Severe hemophilia A or B without inhibitors evidenced by:
 - a. A central laboratory measurement or documented medical record evidence of FVIII $<$ 1% or FIX level \leq 2% at Screening.
 - b. On-demand use of factor concentrate to manage bleeding episodes for at least the last 6 months prior to Screening, and meet each of the following criterion:
 - Nijmegen modified Bethesda assay inhibitor titer of $<$ 0.6 BU/mL at Screening
 - No use of BPAs to treat bleeding episodes for at least the last 6 months prior to Screening
 - No history of immune tolerance induction therapy within the last 3 years prior to Screening
3. A minimum of 6 bleeding episodes requiring factor concentrate treatment within the last 6 months prior to Screening.

-
4. Willing and able to comply with the study requirements and to provide written informed consent and assent in the case of patients under the age of legal consent, per local and national requirements.

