8.2.1. Populations to be Analyzed

The populations (analysis sets) are defined as follows:

- Intent-to-treat (ITT) Analysis Set: All randomized patients. All by-treatment analyses based on the ITT analysis set will be according to the randomized treatment arm.
- Safety Analysis Set: All patients who received at least 1 dose of fitusiran or were randomized to on-demand arm. All by-treatment analyses based on the safety analysis set will be according to the actual treatment received.
- Per-protocol Analysis Set: All patients in the ITT set who had no major protocol deviations. Major deviations will be specified in the SAP.
- PK Analysis Set: All patients who receive at least 1 dose of fitusiran and have at least one postdose blood sample for PK parameters and who have evaluable PK data.
- Operative Procedure Analysis Set: All patients who received at least 1 dose of fitusiran and underwent at least 1 operative procedure during the study.

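### The SAP's per-protocol deviation item for inclusion criterion 2 does not match the protocol: it omits the medical-record route and loosens an all-of rule to a one-of rule

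*SAP*

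**What the plan says.** **Protocol.** Inclusion criterion 2 (Section 5.1) has two limbs.

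- 2a, severity: "A central laboratory measurement or documented medical record evidence of FVIII" below 1%, or of FIX at or below 2%. The synopsis gives the same two routes: "Diagnosis of severe hemophilia A or B will be based on a central laboratory measurement or documented medical record evidence".
- 2b: on-demand factor use for at least 6 months before Screening, "and meet each of the following criterion". Three conditions follow: inhibitor titer below 0.6 BU/mL, no BPA use in 6 months, no ITI in 3 years.

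Section 8.2.1 defines the per-protocol set as ITT patients without major deviations and leaves the detail to the other document: "Major deviations will be specified in the SAP".

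**SAP.** Section 4 opens with a broad category, "Failure to meet key eligibility criteria, which will be identified prior to database lock", and then lists detailed major or critical deviations. The item for inclusion 2 is a negated sentence, "The subject does not have severe hemophilia A or B without inhibitors as evidence by", followed by two bullets.

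- The first begins "A laboratory FVIII level" and gives the same cut-offs at Screening. It has no medical-record alternative.
- The second gives on-demand use, then "or meeting one of the following criteria", then the same three conditions.

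The version 3 entries in SAP Section 2.6 record that detailed deviations were added to the per-protocol definition. They give no reason for departing from the protocol's wording of this criterion.

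**The concern.** Because the protocol delegates the list of major deviations, SAP Section 4 is the operative definition of the per-protocol set. That set is used to repeat the efficacy analysis (SAP 6.3.1.2) and for a set of baseline summaries (SAP 6.2). A per-protocol repeat is useful when it shows the result in patients who met the entry criteria. Here the stated rule differs from those criteria in two ways that act in opposite directions. The severity bullet is narrower than the protocol and can mark an eligible patient as a deviator. The second bullet, read literally, is wider and lets patients pass this item who do not meet the trial's definition of being without inhibitors.

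At stake is whether the per-protocol set is uniquely determined by the text and agrees with the protocol. The primary result is not at stake.

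**Working it through.** No figure in the plan is in dispute, so the check is one of logic.

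**Inputs, side by side**

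| Element | Protocol 5.1 | SAP Section 4 item |
|---|---|---|
| Severity evidence | Central laboratory (L) or medical record (M) | Laboratory level at Screening (L) only |
| On-demand use, 6 months (O) | Required | One of four alternatives |
| Titer below 0.6 BU/mL (T) | Required | One of four alternatives |
| No BPA use, 6 months (B) | Required | One of four alternatives |
| No ITI, 3 years (I) | Required | One of four alternatives |

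L is treated as the same condition in both columns, although the SAP does not say that the laboratory must be central.

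**Rules**

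- Protocol: (L or M) and O and T and B and I.
- SAP, literal reading: L and (O or T or B or I).
- SAP, charitable reading (failing any one element is a deviation): L and O and T and B and I.

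**Counts over the 2^6 = 64 combinations**

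- Protocol: 3 of the 4 L/M combinations × 1 of the 16 O/T/B/I combinations = 3 eligible.
- SAP literal: 2 × 15 = 30 pass.
- Passing both: 2 × 1 = 2.
- Pass the SAP item but ineligible under the protocol: 30 − 2 = 28.
- Eligible under the protocol but flagged by the SAP item: 3 − 2 = 1. This is the patient with M but not L who meets all four other conditions.
- Total disagreement: 28 + 1 = 29 of 64.
- SAP charitable: 2 × 1 = 2 pass, both eligible. Wrongly passed falls to 0; wrongly flagged stays at 1.

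**Among patients with on-demand use.** T, B and I give 8 combinations. The protocol accepts 1. The literal SAP bullet accepts all 8, because on-demand use alone satisfies it.

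**With the item reworded** as failing (L or M), O, T, B or I, the rule matches the protocol in all 64 combinations.

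**Size of one misclassified patient.** Protocol Section 1.3 plans 40 on-demand and 80 fitusiran patients: 1/40 = 2.5% and 1/80 = 1.25%, about 1.3%.

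**What is untouched.** The primary analysis uses the ITT set (SAP 6.3.1.1), and nothing in the testing order (SAP 5.7) depends on the per-protocol set. The sample size reproduces without it. With means 18 and 4, SDs 14 and 6, and 32 and 64 evaluable patients, the log rate ratio is ln(18/4) = 1.504. Its SE is √[(14/18)²/32 + (6/4)²/64] = 0.2325, so z = 6.47 and power exceeds 99.9%. Giving both arms the larger dispersion over one year, (36 − 4)/16 = 2.0, gives SE = √[(1/18 + 2)/32 + (1/4 + 2)/64] = 0.315 and power of 99.8%. Both agree with the stated figure of more than 90%, and 96/(1 − 0.2) = 120.

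**The case against.** The best answer has three parts.

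1. **The second bullet is a slip.** The item lists failures, so its connector is most sensibly read as a botched way of saying that one of the conditions is not met. A patient with a titer of 0.6 BU/mL or more also contradicts the item's own stem. This may well be the intent, and on that reading no ineligible pattern passes. It remains a repair by the reader, and a prespecified analysis set should not depend on which reading the programmer takes.

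2. **Other text catches the violators.** The broad eligibility category in Section 4 would cover an inhibitor, BPA or ITI violation. SAP 5.9 has deviations classified by medical review, in a file finalized before the primary analysis. This is a real safeguard. It rests on key criteria that are still to be identified, while the detailed list is the concrete specification.

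3. **A patient enrolled on medical-record evidence has no deviation.** SAP 5.9 defines a deviation as a departure from the protocol, and such a patient complied with 2a. The SAP's bullet also speaks of a laboratory level without requiring the central laboratory. This softens the point, but an explicit laboratory-at-Screening item still conflicts with 2a on either reading of the second bullet.

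A reader might go further and infer that the wrong patients are in fact kept and removed. The documents do not show this. No affected patient is known, and anyone wrongly kept must first have been randomized against the protocol. A reader might also suppose that recent factor treatment raises Screening levels and so triggers the laboratory bullet; neither document states that mechanism. Nor is 28 of 64 a proportion of patients: it counts unweighted logical patterns.

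**Conclusion.** The mismatch is established from the text. The loss of the medical-record route holds on either reading of the SAP item. The failure to flag a titer, BPA or ITI violator holds only on the literal reading, and the broad category or medical review could still remove that patient.

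The consequence is confined to the per-protocol set: the repeat of the efficacy analysis and the baseline summaries for that set. Alpha, sample size and the ITT primary analysis do not change. The number of patients concerned is not in the documents. The 2.5% and 1.3% figures assume the planned arm sizes of 40 and 80, before any per-protocol exclusions. This is a correction worth making because the stated rule is wrong and the repair is nearly free, not because a result is known to be distorted.

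**What to change.** Before database lock, replace the SAP Section 4 item for inclusion 2 with a deviation defined as randomized despite failing **any one** of:

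- (a) central laboratory or documented medical-record evidence of FVIII below 1% or FIX at or below 2%;
- (b) on-demand factor use for at least the last 6 months before Screening;
- (c) inhibitor titer below 0.6 BU/mL at Screening;
- (d) no BPA use in the last 6 months before Screening;
- (e) no ITI in the last 3 years before Screening.

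This mirrors protocol Section 5.1 element by element. The cost is a wording change and an entry in the SAP 2.6 history table. No new data are needed, since every element is already an entry criterion. If lock has passed, state and justify the corrected rule in the clinical study report, as protocol Section 8.2 provides for changes of method.
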